9.4.5 Interim Analyses and Data Monitoring

An interim analysis is planned to trigger early interaction with regulatory authorities. The data cutoff date is determined such that approximately half of enrolled patients will have received at least one post-baseline tumor assessment.

The primary analysis will be performed after all enrolled patients have been followed up for a sufficient amount of time, defined as with at least two post-baseline tumor assessments. The primary analysis may be updated upon request from regulatory authorities.

10 Study Administration

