| | Up to 28 days prior to first dose | D1 ±2 Days | D8 ±2 Days | D15 ±2 Days | D22 ^d ±2 Days | ±2 Days | EOT ^a ≤ 7 days | D 28 ±7 days | |
| Informed Consent ^e | X | | | | | | | | |
| Inclusion/exclusion criteria | X | | | | | | | | |
| Medical, surgical, malignancy history | X | | | | | | | | |
| Molecular Pathology Report(s) describing RET and other alterations ^f | X | | | | | | | | |
| Archived tumor tissue or fresh biopsy ^g | X | | | | | | | | |
| Physical examination and ECOG ^h | X | X | X | X | | D1 C2, 3, 4, 5, etc. | X | X | |
| Vital signs ⁱ | X | X ^j | X ^j | X ^j | | D1 C2, 3, 4, 5, etc. | X | X | |
| 12-lead ECG ^k | X | X | X | | | D1 C2-6 and every 12 weeks | X | X ^l | |
| Urine or serum pregnancy test ^m | X | X | | | | D1 C2, 3, 4, 5, etc. | | | |
| Hematology ⁿ | X | X | X | X | | D1 C2, 3, 4, 5, etc. | X | X | |
| Serum chemistries ^o | X | X | X | X | | D1 C2, 3, 4, 5, etc. | X | X | |
| Liver function tests ^p | | | | | | C2D15 and C3D15 | | | |

| Visit Window | Screening | Cycle 1 | | | | Cycle 2-higher | SFU ^b | | LTFU ^c |
|--|-----------------------------------|---------------|---------------|----------------|-----------------------------|--|------------------------------|-----------------|-------------------|
| | Up to 28 days prior to first dose | D1 ±2 Days | D8 ±2 Days | D15 ±2 Days | D22 ^d ±2 Days | ±2 Days | EOT ^a ≤ 7 days | D 28 ±7 days | |
| Coagulation ^q | X | X | | | | | | | |
| Thyroid panel ^t | X | | | X | | D1 of odd cycles beginning with C3 (C3, 5, 7, etc.) | | | |
| Urinalysis ^s | X | | | X | | D1 C2, and as clinically indicated. | X | X | |
| Calcitonin, CEA (MTC only) ^t | X | X | | X | | D1 C2 and odd-numbered cycles, starting with C3 through C13. Every 12 weeks thereafter (±7 days of each radiologic disease assessment) | X | | |
| Thyroglobulin (non-MTC thyroid cancers only) ^u | X | X | | X | | D1 C2 and odd-numbered cycles, starting with C3 through C13. Every 12 weeks thereafter (±7 days of each radiologic disease assessment) | X | | |
| Blood cortisol, ACTH, 24-hour urine for free cortisol ^v | X | X | | X | | D1 C2 and odd-numbered cycles, starting with C3 through C13. Every 12 weeks thereafter (±7 days of each radiologic disease assessment) | X | | |
| Disease assessment ^w | X | | | | | Perform assessments at week 4 (±7 days, optional) and week 8 (±7 days) and then every 8 weeks (±7 days) until week 48 following C1D1 and then every 12 weeks (±7 days) | X ^x | | X ^y |

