| Confirmatory disease assessment ^z | | | | | | At least 4 weeks post 1 st PR | | | |
| Blood sample for intensive PK ^{aa} | | X | X | | | | | | |
| Blood sample for PopPK ^{bb} | | X | | | | D1 of each cycle Predose sample to be drawn | | | |
| EORTC QLQ-C30 ^{cc} | | X | | | | Every 8 weeks (±7 days) starting with D1 C3 through D1 C13. Every 12 weeks (±7 days) thereafter | X | | |

| Visit Window | Screening | Cycle 1 | | | | Cycle 2-higher | SFU ^b | | LTFU ^c |
|--|-----------------------------------|---------------|---------------|----------------|-----------------------------|----------------------|------------------------------|-----------------|-------------------|
| | Up to 28 days prior to first dose | D1 ±2 Days | D8 ±2 Days | D15 ±2 Days | D22 ^d ±2 Days | ±2 Days | EOT ^a ≤ 7 days | D 28 ±7 days | |
| Dispense selpercatinib | | X | | | | D1 of each cycle | | | |
| Selpercatinib administration | | | | | | | | | |
| Patient dosing diary | | | | | | | | | |
| Patient bowel diary (MTC only) ^{dd} | | X | X | X | X | D1 C2, 3, 4, 5, etc. | X | | |
| Adverse events ^{ee} | | | | | | | | | |
| Concomitant medications ^{ff} | | | | | | | | | |
| Survival ^{gg} | | | | | | | | X | X |

Abbreviations (for Table 7-1 and Footnotes): ACTH-adrenocorticotrophic hormone; AE-adverse event; ALP-alkaline phosphatase; ALT-alanine aminotransferase; AST-aspartate aminotransferase; BUN blood urea nitrogen; C-cycle; CEA carcinoembryonic antigen; CR complete response; CT-computed tomography; D-day; ECG electrocardiogram; ECOG-Eastern Cooperative Oncology Group; EORTC QLQ-C30-European Organization for Research and Treatment of Cancer Quality of Life Questionnaire-Core 30; EOT-End of Treatment; IV intravenous; LDH lactate dehydrogenase; LTFU long-term follow up; MTC medullary thyroid cancer; MRI magnetic resonance imaging; PD-progressive disease; PK pharmacokinetics; PR partial response; RBC-red blood cell; SAE-serious adverse event; SFU safety follow-up; TSH-thyroid-stimulating hormone; T3-free triiodothyronine; T4-free thyroxine; WBC white blood cell.

- End of Treatment (EOT): +7 days of the last dose or the decision to terminate treatment. If lab testing is performed ≤7 days prior to EOT, repeat testing does not need to occur on EOT.
- Safety Follow-Up (SFU): 28 days (±7 days) after last dose of study drug.
- Long-Term Follow-Up (LTFU): approximately every 3 months (±1 month) for up to two years after the last dose of study drug.
- Telephone contact for safety.

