- w. Baseline disease assessment with radiographic tumor measurements using CT or MRI of chest, abdomen, and pelvis; And any other areas with suspected disease involvement within 28 days of C1D1 as clinically indicated. Brain imaging is required at baseline for all RET fusion-positive patients, patients with a history of CNS metastases, or other patients if clinically indicated and subsequent serial scans if brain metastases are present at baseline (MRI preferred, CT with contrast is acceptable if MRI contraindicated). Required only for patients with nonmeasurable bone disease identified at baseline or if clinically indicated. For each modality, IV and oral contrast should be utilized unless there is a clear contraindication (e.g., decreased renal function or allergy that cannot be addressed with standard prophylactic treatments). In the absence of known or suspected disease involvement, head and neck CT/MRI scans are not required for malignancies other than those originating in the head and neck region. Other areas of scanning may also differ depending on disease type. Post-baseline scans should be performed every 8 weeks (± 7 days) until week 48 and every 12 weeks (± 7 days) thereafter, including imaging of the chest, abdomen, and pelvis, using the same modality(ies) as used for baseline imaging assessment until PD, withdrawal of consent, or initiation of a new anticancer therapy(ies). Additionally, any studies performed at baseline that are positive for sites of disease should be repeated at all post-baseline assessments. Additional studies can also be performed as clinically indicated. In addition, Investigators may conduct an initial tumor evaluation on week 4 (± 7 days) and a confirmatory tumor evaluation a minimum of 4 weeks (i.e., 28 days) after the first tumor evaluation that shows a CR or PR by RECIST 1.1, if consistent with local regulatory authority requirements. In addition, an initial post baseline assessment on week 4 (± 7 days) is encouraged if consistent with regulatory guidelines. If a scan is performed on week 4, the next scan should continue according to the schedule above (beginning at week 8). For patients who continue to receive study treatment beyond progression, post PD scans to determine tumor disease assessment should be performed within 8 weeks (± 7 days) of initial PD (PD₁) and every 8 weeks (± 7 days) thereafter until subsequent PD (PD₂), withdrawal of consent, or initiation of a new anticancer therapy(ies). Additional scans can be performed as needed. All scans (including any unscheduled scans performed during the study) will be collected and stored at a central facility to permit central reviewer assessment. Please see the Site Imaging Manual for guidelines on how the various imaging studies should be performed.

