- x. If not performed within the last 8 weeks.
- y. Patients who discontinue study drug for reasons other than PD (e.g., AE, noncompliance, etc.) may (but for practical reasons and to minimize patient inconvenience, are not required to) undergo additional disease assessment by imaging (as specified above until PD, withdrawal of consent or initiation of a new anticancer therapy(ies)).
- z. Confirmatory scans: Minimum of 4 weeks (e.g., 28 days) after the first tumor evaluation showing a CR or PR by RECIST 1.1, if permitted by regulatory authorities. The next scan should continue according to the schedule above.
- aa. For 12 subjects in intensive PK testing, PK test performed on C1D1: Up to pre-dose, and post-dose 1 hour (± 15 minutes), 2 hours (± 15 minutes), and 4 hours (± 15 minutes), 8 hours (± 30 minutes) and 12 hours (± 30 minutes), C1D8: Up to pre-dose, and post-dose 1 hour (± 15 minutes), 2 hours (± 15 minutes), and 4 hours (± 15 minutes) and 8 hours (± 30 minutes).
- bb. For all enrolled subjects in PopPK testing, PK test performed on each cycle D1 predose.

- cc. EORTC QLQ-C30. The questionnaires should be answered by the subject to the best of his/her ability, prior to receiving drug on C1D1 and preferably prior to learning the results of the radiologic disease assessment for subsequent cycles.
- dd. Only for patients with a diagnosis of MTC and diarrhea at baseline. Two patient bowel diary cards will be dispensed on C1D15. The questionnaires should be answered by the subject to the best of his/her ability.
- ee. AEs and SAEs should be recorded from the time that written informed consent has been obtained through the SFU Visit.
- ff. Concomitant, ongoing medication(s) plus those administered within 14 days prior to the planned start of treatment.
- gg. Patients will be followed for survival status, date of progression, and subsequent anticancer therapy(ies) by telephone or other method.

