- Thyroglobulin: for patients with non-MTC thyroid cancer only, unless not measurable due to presence of anti-thyroglobulin antibodies): Day 1 of C2 and odd-numbered cycles, starting with C3 through C13, and every 12 weeks thereafter (± 7 days of each radiologic disease assessment). For each patient, all tests for thyroglobulin should be performed in the same laboratory to minimize intra-patient, lab-to-lab variability in their measurement.
- Blood cortisol, ACTH, 24-hour urine for free cortisol: for patients with Cushing's disease related to their cancer. Day 1 of C2 and odd-numbered cycles, starting with C3 through C13, and every 12 weeks thereafter (± 7 days of each radiologic disease assessment). If done, urine collection should begin pre-dose.
- Radiographic disease assessment: every 8 weeks (± 7 days) beginning with C3D1 through C13D1, and every 12 weeks (± 7 days) thereafter until PD, withdrawal of consent, or initiation of a new anticancer therapy(ies), including imaging of the chest, abdomen, and pelvis, utilizing the same modality(ies) as used for the baseline imaging assessment. Additionally, any studies performed at baseline that are positive for sites of disease should be repeated at all post baseline assessments. Additional studies can also be performed as clinically indicated. Please refer to the Imaging Manual for guidelines on how the various imaging studies should be performed.

Notes:

- Patients who discontinue study drug for reasons other than PD (e.g., AE, noncompliance, etc.) may (but, for practical reasons and to minimize patient inconvenience, are not required to) have scans performed and collected as defined above.
- Post-baseline imaging of the brain using the same modality as at baseline should be performed for patients with evidence of CNS disease at baseline and if clinically indicated.
- If consistent with local regulatory guidelines, an initial post-baseline assessment after 4 weeks of treatment (± 7 days) is encouraged. If this scan is performed, the next scan should continue according to the schedule above (beginning at C3D1).
- If consistent with local regulatory guidelines, confirmatory imaging a minimum of 4 weeks (e.g., 28 days) after the first imaging studies that demonstrate a tumor CR or PR by RECIST 1.1 is encouraged. If this scan is performed, the next scan should continue according to the schedule above.

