6.14. Interim Analyses and Data Monitoring

An interim analysis is planned to trigger early interaction with regulatory authorities. The data cutoff date is expected to be 31 July 2020, determined such that approximately half of enrolled patients will have received at least one post-baseline tumor assessment.

The primary analysis will be performed after all enrolled patients have been followed up for a sufficient amount of time (with at least two post-baseline tumor assessments, except for patients discontinued early). The primary analysis may be updated upon request from regulatory authorities.

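### The primary-analysis trigger of two post-baseline scans does not exclude the optional week-4 scan, so it can be met before a week-8 response can be confirmed

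*Protocol*

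**What the plan says.** **Trigger.** Protocol 9.4.5 treats the data as ready when all enrolled patients have been "followed up for a sufficient amount of time, defined as with at least two post-baseline tumor assessments". SAP 6.14 states the condition as "with at least two post-baseline tumor assessments, except for patients discontinued early". Neither gives a minimum time since first dose, says which scans count, or mentions confirmation. Both allow the analysis to be updated if regulators ask, and neither names another ground for an update.

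**Scans.** The disease-assessment row of Protocol Table 7-1 reads "Perform assessments at week 4 (±7 days, optional) and week 8 (±7 days) and then every 8 weeks (±7 days", continuing to week 48. Note w to that table says "Investigators may conduct an initial tumor evaluation on week 4" and goes on to encourage "an initial post baseline assessment on week 4". Section 7.3 likewise encourages "an initial post-baseline assessment after 4 weeks of treatment". Note w and Section 7.3 make this scan subject to local regulatory rules, and both leave the week-8 scan in place.

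**Confirmatory scan.** Table 7-1 has a separate row for it, "At least 4 weeks post 1" (the first PR). Note z sets a minimum of 4 weeks "after the first tumor evaluation showing a CR or PR by RECIST 1.1, if permitted by regulatory authorities". Note w words this scan as something investigators may do, and Section 7.3 as something encouraged.

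**Endpoint.** In Protocol 9.4.3 and SAP 6.9.2.1, ORR is confirmed CR or PR divided by the whole analysis population. SAP 6.9.2.1 requires the repeat assessment at least 28 days after response is first seen, and at least 42 days on study for stable disease. SAP 6.9.6 counts stable disease toward CBR only from 16 weeks, measured from first dose.

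**The concern.** A readiness rule should ensure that the primary endpoint can be evaluated in every patient still being imaged. This one counts scans. It does not count opportunities to confirm a response. Because the week-4 scan is described as a post-baseline assessment, weeks 4 and 8 together meet the rule, although a response that first appears at week 8 has had no chance to be confirmed.

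Confirmed ORR by IRC is the only primary endpoint, and Protocol 9.3 judges the result by the lower limit of its exact 95% interval. SAP 6.9.1 runs the primary analysis separately by tumor type as data warrant, so a denominator can be smaller than a cohort and each unresolved response then weighs more.

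**Working it through.** **1. The plan's own precision figure.** Table 9-1 gives a lower limit of 0.23 for n = 20 and ORR 0.45. The Clopper-Pearson lower limit is the 0.025 quantile of a Beta(x, n − x + 1) distribution. With x = 9 and n = 20 this is 0.231, which agrees. All 42 cells of the table reproduce to within 0.005, taking x = n × ORR where that is not a whole number.

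**2. Scan windows.** Days elapsed since first dose = 7 × week ± 7 (Table 7-1).

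| Scan | Window (days) |
|---|---|
| Week 4 (optional) | 21–35 |
| Week 8 | 49–63 |
| Week 16 | 105–119 |

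**3. Earliest date on which the trigger is met.** With scans at weeks 4 and 8, a patient has two post-baseline assessments at day 49–63.

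**4. Response first seen at week 8.** Earliest confirmation is 49 + 28 = day 77 to 63 + 28 = day 91, which is 28 days after the trigger is already met. Protocol Table 11-9 has no row for a PR with no later scan. The nearest row, PR followed by a non-evaluable assessment, gives SD if the minimum SD duration is met and NE otherwise. Day 49 exceeds 42, so the result is SD. Either way the patient is a non-responder who stays in the denominator.

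**5. Response first seen at week 4.** The gap to the week-8 scan runs from 49 − 35 = 14 to 63 − 21 = 42 days. It reaches 28 days in 120 of the 225 day combinations inside the two windows. That is a count of combinations, not a probability. At nominal timing the gap is exactly 28 days and the response can be confirmed.

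**6. CBR.** By the SAP 6.1.2 formula, weeks = (end − start + 1)/7. A scan 63 days after first dose gives 64/7 = 9.1 weeks, short of 16.

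**7. Effect of each pending response.** Counts of 13 to 17 out of 20 correspond to the 64% to 85% ORRs quoted in Protocol 1.5. A count of 10 is added as a less favorable case. The subgroup of 10 is an assumption, taken as the smallest n in Table 9-1.

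| n | Eventual responders | One pending | ORR | Exact lower limit | Fall in limit |
|---|---|---|---|---|---|
| 20 | 17 | 16 | 0.85 to 0.80 | 0.621 to 0.563 | 0.058 |
| 20 | 13 | 12 | 0.65 to 0.60 | 0.408 to 0.361 | 0.047 |
| 20 | 10 | 9 | 0.50 to 0.45 | 0.272 to 0.231 | 0.041 |
| 10 | 7 | 6 | 0.70 to 0.60 | 0.348 to 0.262 | 0.085 |

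Falls were taken before rounding. Two pending responses from 13/20 give 0.55 with a limit of 0.315, and three give 0.50 with 0.272.

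**The case against.** The strongest reply is that the trigger is a floor. It covers all enrolled patients, about 75 including up to 25 in Cohort 3, who are outside the primary ORR population. One continuing patient without a week-4 scan generally holds the analysis until that patient's week 16 (day 105–119), unless a confirmatory or unscheduled scan supplies the second assessment. No primary cutoff date is fixed, and nothing says the sponsor will cut at the minimum. Harm needs a primary-population patient near minimum follow-up, a week-4 scan in that patient, a response not yet confirmable, and no one else still waiting. This stands. It limits how often the problem can arise, but whether the cutoff is in fact delayed depends on which optional scans were done.

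Second, the schedule already contains confirmatory scans, and their row in Table 7-1 is not marked optional. That reduces the problem, but the trigger does not wait for them.

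Third, the bias is conservative, the study is single-arm, and Protocol 9.3 describes a preliminary assessment. From 13/20 it would take four pending responses to fall to 9/20, the 45% reference in Protocol 9.3. This also stands, and it limits the weight of the point.

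A reader might infer that the primary analysis is planned at 7 to 9 weeks of follow-up, or that the reported ORR will be materially too low. The documents support neither. They set a minimum and no date, and they do not give the number of patients near that minimum. Nor can the rule create a false impression of activity, because missing confirmation only removes responders.

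**Conclusion.** The point holds as a gap in the stated sufficiency rule. Two post-baseline assessments do not guarantee that confirmed ORR can be evaluated in a patient whose scans were at weeks 4 and 8, and SAP 6.14 does not close the gap.

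The effect is downward, confined to late-enrolled patients with a week-4 scan, and arises only if the cutoff falls near the floor while no continuing patient has to wait for week 16. The total effect cannot be derived. The effect per pending response can: 5 points of ORR and about 0.04 to 0.06 of the lower limit at n = 20, or 10 points and 0.085 in an assumed subgroup of 10 going from 7 to 6 responders. This is a cheap improvement and not a flaw that undermines the design.

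**What to change.** In Protocol 9.4.5 and SAP 6.14, define the trigger as every enrolled patient having at least two post-baseline assessments at week 8 (with its window) or later and at least 28 days apart, except patients who have progressed, died or discontinued imaging follow-up. State that a confirmatory scan at least 28 days after first response counts and that the week-4 scan does not.

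The week-8 and week-16 scans are 105 − 63 = 42 to 119 − 49 = 70 days apart, so a week-8 response can always be confirmed by week 16, or earlier by a confirmatory scan from day 77–91. A patient who misses week 8 qualifies on week 16 plus a later scan at least 28 days after it.

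At the cutoff, report the number of IRC responses pending confirmation and the number of patients with ongoing stable disease of less than 16 weeks. Both counts are still needed after the change. A response first seen at week 16 cannot be confirmed before day 133–147. A week-16 scan at days 105–110 gives only 106/7 = 15.1 to 111/7 = 15.9 weeks.

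**Cost.** One amended definition in each document and two table entries. The cutoff may move up to about 8 weeks beyond the literal minimum (nominal day 56 to day 112), and not at all if a continuing patient already has to wait for week 16. A week-4 response already confirmed at week 8 would still wait for one more scan. Responses first seen at the last scan before cutoff remain pending under any rule of this kind.

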10.1 Regulatory and Ethical Considerations

- This study will be conducted in accordance with the protocol and with the following:
 - Consensus ethical principles derived from international guidelines including the Declaration of Helsinki and Council for International Organizations of Medical Sciences (CIOMS) International Ethical Guidelines
 - Applicable ICH Good Clinical Practice (GCP) Guidelines
 - Applicable laws and regulations
- The protocol, protocol amendments, ICF, Investigator Brochure, and other relevant documents (e.g., advertisements) must be submitted to an IRB/IEC by the investigator and reviewed and approved by the IRB/IEC before the study is initiated.
- Any amendments to the protocol will require IRB/IEC approval before implementation of changes made to the study design, except for changes necessary to eliminate an immediate hazard to study participants.
- The investigator will be responsible for the following:
 - Providing written summaries of the status of the study to the IRB/IEC annually or more frequently in accordance with the requirements, policies, and procedures established by the IRB/IEC
 - Notifying the IRB/IEC of SAEs or other significant safety findings as required by IRB/IEC procedures
 - Providing oversight of the conduct of the study at the site and adherence to requirements of 21 CFR, ICH guidelines, the IRB/IEC, European regulation 536/2014 for clinical studies (if applicable), and all other applicable local regulations

After reading the protocol, each principal investigator will sign the protocol signature page and send a copy of the signed page to a Lilly representative.

The CSR coordinating investigator will sign the final CSR for this study, indicating agreement that, to the best of his or her knowledge, the report accurately describes the conduct and results of the study.

